8.3.3 Reporting Unanticipated Problems To Participants

For all UPs participants will be informed via mailing at the end of the study. Any UP deemed study intervention related will be included in the informed consent for subsequent participants.

9 STATISTICAL CONSIDERATIONS

9.1 Statistical Hypotheses

The primary hypotheses are: (1) Scores on the Genetics Knowledge Scale (GKS) will not differ between virtual pre-test genetic counseling and IMAGINE-PD methods, and (2) Scores on the genetic counseling satisfaction scale and test-related distress scale (IES-R) will not differ between telephone and telegenetic results disclosure methods. The primary analyses of knowledge will be measured by the GKS at 4 weeks after pre-test counseling; Satisfaction by the GCSS score between genetic counseling groups immediately after pretest and disclosure counseling; and test-related distress by the IES-R score at 3 months between post disclosure. The null hypothesis is that these methods differ.

Secondary hypotheses include IES-R at 6 months between genetic counseling groups, scores on affect, outcomes, and quality of life scales at 3 and 6 months.

9.2 Sample Size Determination

The difference in IES-R between groups after genetic disclosure counseling is used to determine sample size. A clinically significant difference in IES-R score is not defined. Sample size is determined from previously reported normative data of the IES-R in a community sample of N=154 non-PTSD ex-service members, demonstrating a mean of 1.82 (SD=1.05).¹⁶ A range of equivalence limits, the difference in standard deviation beyond which a significant difference would be considered relevant, are demonstrated in **Table 3** at alpha = 0.05 and power of 80%.²⁵ A sample size of N=80/counseling group (divided between PD+gene+ (45%), PD+gene- (45%), and

PD-gene+ groups (10%)), with an expected attrition of 15-20%, would allow for analysis of the primary outcome at a conservative 0.5-0.75 SD equivalence limit, and allow genetic and PD-subgroup analysis.

8		8
Equivalence limit (SD)	Per Group	Total Sample Size
0.5	80	320
0.75	36	132
1	20	80

Table 3. Sample Size Estimates.

9.3 **Populations for Analyses**

Analyses will be conducted for all randomized participants *in the* Intention-to-Treat (ITT) Analysis Dataset, as well as the Per-Protocol Analysis Dataset defined a subset of the participants in the full analysis (ITT) set who complied with the protocol sufficiently to ensure that these data would be likely to represent the effects of study intervention according to the underlying scientific model (e.g., participants who complete the 3-month study visit).

Protocol 843748-
GET VIRTUAL PD
IMAGINE-PD

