1 STUDY SUMMARY

1.1 Synopsis

Title:	GEnetic counseling Through VIRTUAL visits in Parkinson's Disease
Short Title:	GET Virtual PD
Study Description:	This research tests novel approaches to pre-test counseling and post-test disclosure of genetic information in people with PD. Participants will be randomized to receive different methods of genetic counseling in a factorial design. In both pre- and post-test counseling phases, novel genetic counseling methods will be compared to telephone genetic counseling to demonstrate equivalence. The primary outcomes will be equivalence on genetics knowledge and outcomes scales, and the revised impact of events scale. The purpose is to develop effective and scalable approaches to genetic counseling. This work is crucial for patient safety and will improve access to care through novel genetic counseling approaches.
Objectives:	The primary objectives of this study are to determine the efficacy of (1) an audiovisual, web-based genetic counseling tool called the Interactive, Multimedia Approach to Genetic counseling to INform and Educate in Parkinson's Disease (IMAGINE-PD), and (2) disclosure of genetic testing results through a real-time, videoconference telegenetics platform compared to telephone counseling.
Primary Endpoints:	Genetics Knowledge Scale 4 weeks after pre-testing counseling, Revised Impact of Events Scale 3 months after genetic results disclosure, Genetic Counseling Satisfaction Scale (GCSS) immediately after disclosure counseling.
Secondary Endpoints:	GCOS, GDS, STAI, PDQ-39, C-SSRS, MoCA
Study Population:	N= 320 (80/counseling group) Parkinson's disease patients seen at the University of Pennsylvania Parkinson's Disease and Movement Disorders Center (PDMDC) who are also enrolled in the PDMDC Genetics Biobanking Protocol (IRB 830237), aged 21 and over.
Phase:	NA

Description of Sites/Facilities	Single-site
Enrolling Participants:	UPENN PDMDC

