9.4 Statistical Analyses

9.4.1 General Approach

Descriptive statistics will be presented as percentages for binary variables, and as means with standard deviations or median with IQR depending on the distribution of the data. For inferential tests, the Type I error will be set at 0.05 using two-tailed tests. Covariates will be determined based on their significance as independent predictors of outcome, although age and sex will be included in all models. Check on normality will be performed through data visualization as well as using appropriate statistical tests of normality (eg Shapiro-Wilks test). Transformation of non-normally distributed continuous variables will be performed, and models will be compared to non-transformed models using non-parametric tests.

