9.4.2 Analysis of the Primary Efficacy Endpoint(s)

The primary endpoint is the score on the IES-R scale, which will be treated as a continuous variable. The primary outcome will be difference in IES-R score between the counseling groups at 3 months post disclosure. A linear regression model accounting for baseline differences in age, sex, and other relevant covariates will be used. Missing data will be handled in 2 ways: an analysis of available data, and using an imputed dataset. Imputation will be performed via multiple imputation using the MICE (Multivariate Imputation via Chained Equations) package. Imputation in this package uses linear and logistic regression to predict missing values. MICE assumes missing values are missing at random, and overall missingness pattern will be assessed using this package. Results will be reported as means with standard errors. Assumptions for each statistical model will be tested. Results will be analyzed using 2 approaches: data transformation and using nonparametric statistical tests, where necessary. Bonferroni correction will be used to correct for multiple-testing comparisons.

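### The plan gives equivalence limits only for the IES-R and does not say whether any limit applies to the other two primary endpoints, the GKS and the GCSS

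*Combined protocol and SAP*

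**What the plan says.** The Synopsis, Section 3 and Table 2 list three primary outcomes: GKS, IES-R and GCSS. The Synopsis entry begins "Genetics Knowledge Scale 4 weeks after pre-testing counseling, Revised Impact of Events Scale 3 months after genetic results disclosure" and adds the GCSS straight after disclosure.

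Section 9.1 turns these into hypotheses of no difference. For pre-test counseling it is "Scores on the Genetics Knowledge Scale (GKS) will not differ between virtual pre-test genetic counseling and IMAGINE-PD methods". For disclosure, the GCSS and IES-R are expected not to differ between telephone and video. The null is that the methods differ, which is an equivalence-type null.

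Section 9.2 opens with "The difference in IES-R between groups after genetic disclosure counseling is used to determine sample size". It states "A clinically significant difference in IES-R score is not defined", cites an IES-R mean of 1.82 (SD 1.05), and tabulates sample sizes for limits of 0.5, 0.75 and 1 SD "at alpha = 0.05 and power of 80" per cent. It concludes that 80 per counseling group "would allow for analysis of the primary outcome at a conservative 0.5-0.75 SD equivalence limit".

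Section 9.4.1 says "the Type I error will be set at 0.05 using two-tailed tests". Section 9.4.2 says "The primary endpoint is the score on the IES-R scale, which will be treated as a continuous variable" and describes a linear regression with Bonferroni correction. Section 9.4.3 covers secondary endpoints. Section 9.4.7 adds that all primary and secondary endpoints are compared with age and sex as covariates.

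No section gives a limit, an SD, a power or a decision rule for the GKS or the GCSS.

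**The concern.** An equivalence null can be rejected only once the smallest difference that matters has been given a number. For the GKS and GCSS the plan supplies none, and the tests it does prescribe are ordinary two-tailed difference tests. Two routes to a conclusion remain open. One is to read a non-significant difference as equivalence. The other is to pick a limit once the results are known.

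The stake is highest for objective 1, the efficacy of IMAGINE-PD, because hypothesis (1) in 9.1 tests it with the GKS. The telephone-versus-virtual satisfaction claim has the same gap. The same data could pass or fail depending on a choice that the plan leaves open.

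**Working it through.** **Inputs from the plan.** 80 per counseling group and 1:1:1:1 allocation (9.2, 6.4); attrition 15-20%, alpha 0.05, power 80%, limits 0.5/0.75/1 SD (9.2); two-tailed 0.05 (9.4.1); Bonferroni, number of tests not stated (9.4.2).

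**Assumptions added here.** Groups are pooled by factor, giving 160 v 160. The full 15-20% attrition applies, giving 160 x 0.85 = 136 or 160 x 0.80 = 128 per level. Bonferroni covers three primary endpoints (0.05/3 = 0.0167). Normal approximation in SD units.

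**Step 1: the plan's own figure.** Two one-sided tests (TOST) at 0.05 per side, 80% power, true difference zero:

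n = 2 x ((1.645 + 1.282)/m)^2, then divided by 0.85 for 15% attrition.

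| Limit m (SD) | n | n/0.85 | Table 3 |
|---|---|---|---|
| 0.5 | 68.5 | 80.6 | 80 |
| 0.75 | 30.4 | 35.8 | 36 |
| 1 | 17.1 | 20.2 | 20 |

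This is close on every row. A two-sided difference formula with 20% attrition gives 78.8/35/20, so the exact formula is not certain. Neither route uses the IES-R mean or SD: the table is in SD units throughout.

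**Step 2: precision per factor level.** SE = sqrt(2/n) = 0.125 SD (n = 128) or 0.121 SD (n = 136). The 90% CI half-width is 1.645 x SE = 0.21 or 0.20 SD. An observed deficit of 0.2 SD then reaches about 0.40-0.41 SD, which is inside a 0.5 SD limit and outside a 0.3 SD limit.

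**Step 3: does the choice of limit decide the verdict?** Suppose a true GKS deficit of 0.4 SD (hypothetical). TOST passes when the estimate lies within m - 1.645 x SE of zero, so P(pass) is approximately Phi((m - 1.645 x SE - 0.4)/SE). For m = 0.5 and n = 128: (0.5 - 0.206 - 0.4)/0.125 = -0.845, so 0.199.

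| Limit (SD) | P(declared equivalent), n = 128 / 136 |
|---|---|
| 0.5 | 0.199 / 0.206 |
| 0.75 | 0.876 / 0.893 |

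Both limits lie in the range that 9.2 names.

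**Step 4: non-significance used instead.** For a true 0.3 SD deficit, P(not significant) is approximately Phi(z - 0.3/SE). At two-tailed 0.05 this is 0.330 / 0.304. At 0.0167 it is 0.498 / 0.468.

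**Step 5: power at true equality if a limit is set.** Power = 2 x Phi(m/SE - z) - 1.

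| Limit (SD) | 90% CI (0.05 per side) | 95% CI (0.025 per side) | 0.05/3 per side |
|---|---|---|---|
| 0.5 | 98-99% | 96-97% | 94-95% |
| 0.4 | 88-90% | 79-82% | 72-76% |

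If single groups of 80 were compared unpooled (64-68 evaluable), a 0.4 SD limit with a 90% CI would have 46-51% power.

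**The case against.** The strongest reply is that Table 3 is in SD units and so could be applied to any continuous scale. That is arithmetically right, and a reader should not infer that the limits cannot carry over: nothing in the documents shows that. What stands is narrower. The plan does not say that they carry over, 9.2 ties them to the IES-R, and it names a range across which the pass rate in Step 3 moves from about 20% to 88-89%.

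A reader might also infer that the GKS is the only primary endpoint judging IMAGINE-PD. The documents do not support that cleanly. Section 9.1 also lists the GCSS immediately after pre-test counseling among the primary analyses, while the Synopsis, Section 3 and the schema place the primary GCSS after disclosure. The passages conflict.

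Nor is the IES-R well specified by contrast. It has a range rather than one limit, and no rule in 9.4 uses it. The GKS and GCSS gap is still separate, because a confidence-interval rule added for the IES-R would leave these two scales with nothing to compare against.

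Two further replies are fair. Sizing a trial on one endpoint is ordinary practice. An analysis model is not wholly absent either, since 9.4.7 covers all primary endpoints, although it supplies no limit.

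Finally, the 0.4 SD and 0.3 SD deficits are hypothetical. Attrition by Visit 2, when the GKS and disclosure GCSS are measured, may be below 15-20%, and Section 7.2 provides for replacement.

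**Conclusion.** The concern holds as a specification gap. Two of the three primary endpoints carry equivalence-type hypotheses, with no stated limit and no rule for deciding them. Followed as written, equivalence on the GKS or GCSS would rest on non-significance, which misses a true 0.3 SD deficit 30-33% of the time (47-50% at 0.05/3), or on a limit chosen afterwards.

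It is not a sample-size failure, and a reader should not take it as one. For a 0.5 SD limit, pooled power is 94-99% depending on the multiplicity rule. At 0.05 per side it drops below 80% only for limits tighter than about 0.36-0.37 SD, and at 0.05/3 for limits tighter than about 0.41-0.43 SD.

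These figures rest on pooling by factor, which 9.1 implies but does not state, on 128-136 evaluable per level, and on three tests for Bonferroni.

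**What to change.** In 9.2 and 9.4:

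1. Define which GKS items are scored as knowledge. Table 2 says the questionnaire also covers attitudes, beliefs and interest.
2. Name one equivalence limit for the GKS (IMAGINE-PD v virtual pre-test) and one for the GCSS, each justified by what difference matters on that scale, and fix both before any comparison by arm. If the 9.2 limits are meant to apply, say so and choose one value.
3. Reconcile whether the primary GCSS is after disclosure only or also after pre-test counseling, and apply the limit to whichever comparisons remain primary.
4. Conclude equivalence only if the CI for the adjusted, pooled factor-level difference lies wholly inside the limit. State the number of tests and match the CI level to the Bonferroni correction in 9.4.2 (for three tests at 0.05/3 per side, a 96.7% CI).
5. State power at that level. For 128-136 per level, a 0.5 SD limit gives 98-99% with a 90% CI and 94-95% at 0.05/3; a 0.4 SD limit gives 88-90% and 72-76%. These show what is feasible and do not by themselves justify either limit.
6. If no limit is set for a scale, report the difference with its CI and make no equivalence claim.

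The cost is some protocol wording and the work of justifying two limits. No added participants are needed at 0.5 SD; a tighter limit under the correction would have less power. The real price is that the sponsor must commit in advance.

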6.4 Measures to Minimize Bias: Randomization and Blinding

Subjects will be randomized 1:1:1:1 into each of the 4 factorial-design groups: IMAGINE-PD/Virtual, IMAGINE-PD/Telephone, Virtual/Virtual, Virtual/Telephone. Participants and investigators will be blinded to the genetic testing results (research or clinic confirmation test) until the disclosure visit. The non-clinical researcher from the MIND study who will provide blinded lists of potential participants will not be involved in study conduct, data collection, patient interaction, or have access to any clinical data collected in the GET Virtual PD study.

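### Section 9.2 calls a 0.5-0.75 SD equivalence limit conservative, but a wider limit is more lenient, no single limit is fixed, and the power is stated for one cell of 80 instead of the 160 vs 160 disclosure comparison

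*Combined protocol and SAP*

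**What the plan says.** Section 9.2 sizes the trial on the IES-R after disclosure. It states that "A clinically significant difference in IES-R score is not defined" and takes its SD from a community sample of ex-service members, "demonstrating a mean of 1.82 (SD=1.05"). It describes an equivalence limit as "the difference in standard deviation beyond which a significant difference would be considered relevant". Table 3 lists limits of 0.5, 0.75 and 1 SD with 80, 36 and 20 per group, "at alpha = 0.05 and power of 80" percent. The text then settles on 80 per counseling group with 15-20% attrition, which it says "would allow for analysis of the primary outcome at a conservative 0.5-0.75 SD equivalence limit" and also permits genetic and PD subgroup analysis.

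Section 6.4 says "Subjects will be randomized 1:1:1:1 into each of the 4 factorial-design groups". Section 9.1 states the IES-R hypothesis as a comparison of telephone with telegenetic disclosure, which is one factor of the two. Section 9.4.2 speaks only of the difference between the counseling groups. Section 9.4.1 says "the Type I error will be set at 0.05 using two-tailed tests". Section 9.4.2 adds a Bonferroni correction without giving the number of tests.

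**The concern.** Three things in section 9.2 do not fit together.

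- **Direction.** The limit is the largest difference still treated as irrelevant. Widening it makes equivalence easier to declare, so 0.75 SD is more lenient than 0.5 SD.
- **A range with no anchor.** The plan gives no clinical reason for either end and does not say which end decides. A result that passes at 0.75 SD and fails at 0.5 SD could be reported either way.
- **Wrong comparison group.** The table's number per group is set equal to one cell of the factorial, but the section 9.1 hypothesis pools two cells on each side. The 80% in section 9.2 is therefore not the power of the planned comparison.

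The IES-R measures test-related distress and is the endpoint that sizes the trial. A claim that two disclosure methods are equivalent on distress means little if a moderate true increase would usually pass.

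**Working it through.** **Inputs.** Limits 0.5, 0.75 and 1 SD; alpha 0.05; power 80%; SD 1.05; 80 per cell; attrition 15-20% (all section 9.2). Four equal cells (section 6.4). Disclosure-method comparison (section 9.1). Assumptions not in the documents: true difference 0, no interaction between the two factors, two one-sided tests (TOST), and three endpoints for Bonferroni (the three primary endpoints of the synopsis). The per-side alpha is not stated, so 0.05 (90% CI) and 0.025 (95% CI) are both shown.

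**1. Reproduce Table 3.** n per group = 2 × ((z(1-α) + z(0.90)) / limit)², with α = 0.05 per side.

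- 0.5 SD: 2 × ((1.645 + 1.282)/0.5)² = 68.5; divided by 0.85 = 80.6 (stated 80)
- 0.75 SD: 30.4; divided by 0.85 = 35.8 (stated 36)
- 1 SD: 17.1; divided by 0.85 = 20.2 (stated 20)

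A one-sided 0.025 non-inferiority formula with 20% attrition fits about as well (79, 35, 20). TOST at 0.025 per side does not (100-107 at 0.5 SD after attrition). Either way, 80 is the size of one side of a two-group comparison at 0.5 SD. The table multiplies it by four cells to reach 320. (Separately, 4 × 36 = 144, not the 132 printed in the 0.75 SD row.)

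**2. The planned comparison.** Each disclosure method occupies two cells: 2 × 80 = 160 per level. After attrition this is 160 × 0.85 = 136 or 160 × 0.80 = 128.

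**3. Power at ±0.5 SD** (t-based TOST, true difference 0):

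| Per-side alpha | 128 per level | 136 per level |
|---|---|---|
| 0.05 | 98% | 99% |
| 0.025 | 96% | 97% |
| 0.05/3 | 94% | 95% |
| 0.025/3 | 89% | 91% |

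At ±0.75 SD power is essentially 100% throughout.

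**4. What ±0.75 SD lets through.** On the plan's SD, 0.5 SD = 0.5 × 1.05 = 0.53 points and 0.75 SD = 0.79 points. With 128 per level and a true rise of 0.5 SD, equivalence is declared 64% of the time at 0.05 per side and 51% at 0.025. With a ±0.5 SD limit, the same true rise passes 5% or 2.5% of the time, which is the test's own error rate.

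**5. Largest observed difference that passes.** The whole interval must lie inside the limit, so this is the limit minus t × √(2/n). With n = 128, √(2/128) = 0.125. For ±0.75 SD: 0.75 - 1.651 × 0.125 = 0.54 SD (0.57 points), or 0.75 - 1.969 × 0.125 = 0.50 SD (0.53 points).

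**6. Limit supported at 80% power.** (z(1-α) + z(0.90)) × √(2/n), for 128-136 per level: about 0.36-0.37 SD at 0.05 per side and 0.39-0.41 SD at 0.025. With Bonferroni over three endpoints it is 0.41-0.43 SD (0.05/3) or 0.45-0.46 SD (0.025/3).

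**The case against.** The sample size is the 0.5 SD row of Table 3, not the 0.75 SD row, and the quoted range leaves out the widest tabulated limit. On that reading, conservative could mean stricter than 1 SD. The text does not say so, and it still leaves 0.75 SD available as a criterion.

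The extra precision also has a stated use, subgroup analysis. PD carriers are 45% of the sample, so 0.45 × 160 = 72 per level, or 58-61 after attrition. Power there at ±0.5 SD is only 70-73% at 0.05 per side. That stands: the sample is not simply surplus, and it argues against tightening the limit merely because the main comparison could bear it.

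Pooling to 160 per level is not beyond dispute. It assumes no important interaction, which the protocol does not address, and section 9.4.2 could be read as comparing single cells. On that reading 64-68 per cell gives 76-79% power at ±0.5 SD (0.05 per side). Section 9.2 must name the comparison in either case.

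Two stronger inferences are tempting and are not supported. A reader might infer that a rise of up to 0.79 points would be reported as equivalence. It would not: 0.79 is the limit itself, and the largest observed difference that passes at 128 per level is 0.53-0.57 points (step 5). A reader might also infer that about 0.4 SD is the correct limit. The arithmetic shows only that the sample supports it. It gives no clinical anchor, and a margin should not move with the way alpha is split. A limit of ±0.43 SD, for instance, has only 70-74% power at 0.025/3 per side.

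**Conclusion.** The point holds. Calling 0.5-0.75 SD conservative is wrong in direction, the range leaves the decision rule unfixed, and the stated 80% power belongs to a single-cell comparison that section 9.1 does not pose for the IES-R. The planned comparison has 96-99% power at ±0.5 SD, still 89-95% under a three-way Bonferroni correction, so nothing in the sample size calls for 0.75 SD. Keeping it raises the chance of passing a true 0.5 SD rise from 2.5-5% to 51-64% at 128 per level. These figures rest on the plan's attrition range, a true difference of 0 for the power values, and no interaction between pre-test and disclosure method. Expressing 0.5 SD as 0.53 points also rests on the SD of 1.05. The documents do not settle which limit at or below 0.5 SD is clinically right.

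**What to change.** In section 9.2:

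1. Delete the word conservative and the 0.75 SD option.
2. Name telephone vs virtual disclosure, pooled over pre-test method, as the comparison that is sized, and state the no-interaction assumption.
3. Fix one equivalence limit no wider than ±0.5 SD before analysis, with its justification and per-side alpha, including whether Bonferroni applies and over how many tests.
4. Replace the power statement with the figure for 128-136 per level from the working table that matches the chosen alpha.

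The sponsor may adopt a tighter limit if it can be justified clinically. The same sample supports about 0.36-0.41 SD at 80% power without Bonferroni, or 0.41-0.46 SD with it.

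The cost is a few sentences and no additional participants. The downside is that a result meeting only 0.75 SD could no longer be called equivalence. A limit below 0.5 SD would also lower the stated power, and more so in the genetic subgroups.

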9.4.7 Sub-Group Analyses

All Primary and Secondary endpoints will be compared using age and sex as covariates in each multivariate model. PD and Gene groups will also be compared.

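### Section 9.2 says the sample size allows subgroup analysis, but the group without PD is too small for any conclusion that counseling modes are equivalent within the stated 0.5-0.75 SD range

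*Combined protocol and SAP*

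**What the plan says.** Section 9.2 bases the sample size on the IES-R. Table 3 gives 80, 36 and 20 per group for equivalence limits of 0.5, 0.75 and 1 SD, "at alpha = 0.05 and power of 80" percent. The subgroup shares follow: "A sample size of N=80/counseling group (divided between PD+gene+ (45%), PD+gene- (45%), and" then "PD-gene+ groups (10%)), with an expected attrition of 15-20" percent. The sentence ends by saying that this size serves the "primary outcome at a conservative 0.5-0.75 SD equivalence limit, and allow genetic and PD-subgroup analysis".

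The only other statement on these subgroups as an analysis is in section 9.4.7: "PD and Gene groups will also be compared". Neither section gives a margin, a test or a power for them, or says whether the aim is equivalence of counseling modes within a subgroup, a difference in mode effect between subgroups, or a plain contrast of one subgroup with another.

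Section 6.4 sets the allocation: "Subjects will be randomized 1:1:1:1 into each of the 4 factorial-design groups". Section 9.1 compares telephone with telegenetic disclosure on the IES-R, which in this design is one level of the disclosure factor against the other, 160 v 160.

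**The concern.** The subgroup remark shares a sentence with an equivalence limit and has no other stated basis, so it is natural to judge it against that limit. Ten percent of 80 is 8 per arm, or 16 per factor level. Both fall below every row of Table 3, including the 1 SD row, which lies outside the range the plan calls conservative.

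Section 4.1 names at-risk carriers without PD as a study group, and section 9.1 hypothesises that the methods will not differ. If the plan says the size allows subgroup analysis, a wide interval or a non-significant difference in this group could be reported as support for equivalence when the data could not have supplied it.

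**Working it through.** **Inputs.** From section 9.2: 80 per counseling group, shares 45/45/10, attrition 15-20%, limits 0.5 and 0.75 SD, alpha 0.05, power 80%. From section 6.4: equal allocation to four arms. Assumed, because the documents do not say: true difference zero, equal SDs, no gain from covariates, no Bonferroni adjustment. Limits are in SD units, so the planning SD of 1.05 cancels.

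**The plan's own figure.** For two one-sided tests at 0.05 each (90% interval), n per group = 2 × ((1.645 + 1.282) / limit)². This gives 68.5, 30.4 and 17.1 for 0.5, 0.75 and 1 SD. Dividing by 0.85 for 15% attrition gives 80.6, 35.8 and 20.2, against 80, 36 and 20 in Table 3. The per-group column reproduces. (The total of 132 in the 0.75 row is not 4 × 36 = 144; this does not affect the point.)

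**Subgroup sizes.** Per arm: 0.45 × 80 = 36, 36 and 0.10 × 80 = 8. Per factor level, two arms pooled: 72, 72 and 16.

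**Formulas, in SD units.** SE = √(2/n). Half-width of the 90% interval = 1.645 × SE. Power = 2Φ(limit/SE − 1.645) − 1, floored at 0.

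Example, PD-gene+ at factor level after 15% attrition: n = 16 × 0.85 = 13.6; SE = 0.383; half-width = 0.63. At 0.5 SD the half-width exceeds the limit, so power is 0. At 0.75 SD, 0.75/0.383 − 1.645 = 0.311, and power is 24%.

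Results after 15% / 20% attrition:

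| Group | Comparison | n per side | Half-width | Power at 0.5 SD | Power at 0.75 SD |
|---|---|---|---|---|---|
| PD-gene+ | factor level | 13.6 / 12.8 | 0.63 / 0.65 | 0 / 0 | 24% / 20% |
| PD-gene+ | arm v arm | 6.8 / 6.4 | 0.89 / 0.92 | 0 / 0 | 0 / 0 |
| PD+gene+ or PD+gene- | factor level | 61.2 / 57.6 | 0.30 / 0.31 | 74% / 70% | 99% / 98% |
| PD+gene+ or PD+gene- | arm v arm | 30.6 / 28.8 | 0.42 / 0.43 | 24% / 20% | 80% / 77% |

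Before attrition, PD-gene+ at factor level has 0% at 0.5 SD and 37% at 0.75 SD, and 0% at both by arm. Each PD group has 82.5% and over 99% at factor level, and 37% and 88% by arm.

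**Smallest size at which the interval can fit.** 2 × (1.645/limit)² = 21.6 per side at 0.5 SD and 9.6 at 0.75 SD. Sixteen per level fails the first; 8 per arm fails both.

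**Difference in mode effect between subgroups** (80% power, two-sided 0.05, multiplier 1.960 + 0.842 = 2.80; k = 0.85 or 0.80):
- Mode by PD: 2.80 × √(2/(144k) + 2/(16k)) = 1.13-1.17 SD.
- Mode by gene within PD: 2.80 × √(4/(72k)) = 0.72-0.74 SD.

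**Plain contrasts between groups**, all arms pooled, same multiplier:
- PD+gene+ v PD+gene- (144 v 144): 2.80 × √(2/(144k)) = 0.36-0.37 SD.
- PD v no PD (288 v 32): 2.80 × √(1/(288k) + 1/(32k)) = 0.57-0.58 SD.

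**The case against.** The strongest reply is that section 9.2 attaches the equivalence limit to the primary outcome only and never says that subgroup analysis means an equivalence test. Read literally, section 9.4.7 compares the PD and gene groups with one another, and for that purpose the size is reasonable. Section 6.2 also acknowledges that few carriers without PD will be selected. This stands as far as it goes: a reader might infer that the plan promises 80% power for equivalence in each subgroup, and the documents do not support that. The point is therefore conditional on what the subgroup analysis is meant to show. But the plan's silence does not make the clause informative, and reading it as a search for heterogeneity does not help the group without PD, where the detectable mode-by-PD interaction exceeds the whole equivalence range.

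Two further inferences would go too far:

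- That the PD gene groups are also too small. They fall short of 80% only at 0.5 SD, and at factor level only after attrition. At 0.75 SD, the other end of the stated range, 36 per arm is exactly the Table 3 figure, and the factor-level comparison has ample power.
- That equivalence at 0.5 SD in the group without PD is impossible whatever the data. That is exact only if the SD is treated as known or the limit scales with the observed SD. With a limit fixed at 0.5 × 1.05 = 0.525 points and a t interval, an unusually small observed SD could produce success, with probability about 0.8% at 16 per level and 0.06% at 8 per arm.

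No passage says that a non-significant subgroup result will be read as equivalence; that is a risk left open, not a stated intention.

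**Conclusion.** The point holds for the group without PD. At the planning SD its size cannot support a counseling-mode equivalence conclusion at 0.5 SD, and at 0.75 SD it does so at best about one time in four after attrition, even if the modes are truly identical. For the two PD groups the claim is sound at 0.75 SD at factor level, borderline there by arm, and short of the plan's power standard at 0.5 SD once attrition is counted.

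The figures use one-sided 0.05 per test, the level that reproduces Table 3. Section 9.4.1 says "the Type I error will be set at 0.05 using two-tailed tests", without saying how that maps to equivalence. At 0.025 per side the picture is worse: after attrition PD-gene+ has 0% at both limits at factor level, and each PD group has 53-58% at 0.5 SD and 96-97% at 0.75 SD. A Bonferroni adjustment covering the subgroups would lower power further.

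The primary disclosure comparison is unaffected: 160 per side gives 98-99% at 0.5 SD after attrition by the same formula. This is an unsupported statement about subgroups that should be corrected; it is not a flaw in the main design.

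**What to change.** In section 9.2, replace the closing clause on subgroups with what the size delivers after attrition, naming the per-side alpha used:

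- PD+gene+ and PD+gene-: counseling modes compared at factor level, 90% interval half-width about 0.30 SD, power 70-74% at 0.5 SD and 98-99% at 0.75 SD.
- PD-gene+: half-width 0.63-0.65 SD at factor level, power essentially 0% at 0.5 SD and 20-24% at 0.75 SD.
- Plain contrasts: about 0.36-0.37 SD detectable for PD+gene+ v PD+gene-, and 0.57-0.58 SD for PD v no PD.

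In both 9.2 and 9.4.7, state that counseling-mode results within PD-gene+ are descriptive (estimate and confidence interval), with no equivalence or no-difference conclusion, and that the two PD groups are analysed at factor level with the power above. Section 9.4.7 should also say which of its comparisons are contrasts between groups and which are counseling-mode comparisons within a group.

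The cost is wording only. No extra participants are needed, and the stated capability becomes less favourable.
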